Window (days)	-28 to 0	--	± 3	± 3	± 3	± 3	± 3	± 3	± 3	± 3	± 3	± 3	± 7	± 7	± 7
Informed consent ^a	X														
Medical, cancer history ^d	X														
Physical examination	X			X	X	X	X	X	X	X	X	X	X	X	
Pregnancy test (serum or urine) ^e	X ^e			X	X	X	X	X	X	X	X	X	X		
ECOG performance status	X			X	X	X	X	X	X	X	X	X	X	X	
Vital signs (see Section 8.2.3) ^f	X	X		X	X	X	X	X	X	X	X	X	X	X	
Body weight	X	X		X	X	X	X	X	X	X	X	X			
Hematology (see Table 10)	X		X	X	X	X	X	X	X	X	X	X	X	X	
Clinical chemistry (see Table 10)	X		X	X	X	X	X	X	X	X	X	X	X	X	
Urinalysis	X		X	X	X	X	X	X	X	X	X	X	X	X	
12-lead ECG	X														
Tumor markers ^g	X			X	X	X	X	X	X	X	X	X	X		
cfDNA (blood) ^h	X			X									X		
Circulating soluble analytes ⁱ	X	X	X	X	X	X							X		
Blood immune biomarkers ⁱ	X	X	X	X	X	X							X		
Stool collection ^j	X			X											
Tumor biopsy ^k	X ^l	As early as possible after the 2nd dose ^k of ipilimumab and after the 4th dose of ipilimumab													
Concomitant medications ^m	X	X	X	X	X	X	X	X	X	X	X	X	X	X	X
Adverse events ^m	X	X	X	X	X	X	X	X	X	X	X	X	X	X	X
Nivolumab administration ⁿ		X		X	X	X	X	X	X ^o	X	X	X			
Ipilimumab administration ⁿ		X		X		X		X							

Tests & Procedures	Screening ^a	On-Treatment Evaluations											End of Treatment	Follow-up	
		C1	C2	C3	C4	C5	C6	C7	C8	C9	C10				
Day	0	D1	D8	D1	D1	D1	D1	D1	D1	D1	D1	D1	15-30 days after last dose	First visit (90 days after last dose) ^b	Q3M for 2 years ^c
Window (days)	-28 to 0	--	± 3	± 3	± 3	± 3	± 3	± 3	± 3	± 3	± 3	± 3	± 7	± 7	± 7
Follow-up for overall survival ^c														X	X
Assess subsequent cancer therapy													X	X	X
Disease assessment ^p	X	Cycle 4 Day 1, then beginning at Cycle 6 Day 1, repeat every 8 weeks (± 7 days) until radiographic progression or the start of subsequent therapy, whichever comes first													

cfDNA = cell-free deoxyribonucleic acid; Cx = Cycle x; ECG = electrocardiogram; ECOG = Eastern Cooperative Oncology Group; Q3M = every 3 months; Q3W = every 3 weeks; Q4W = every 4 weeks; Q6W = every 6 weeks; Q12W = every 12 weeks.

^a Screening evaluations are to be conducted within 28 days of the first dose of protocol therapy. Some screening procedures may occur on Cycle 1 Day 1 as appropriate. Informed consent must be obtained prior to any study-specific procedures and may be obtained prior to the 28-day screening window.

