^b Ninety (90) days after the last dose there is a visit with assessments *if no alternative therapy has started*. If the participant has started alternative therapy within that 90 days after the last dose, the first follow up visit will be contact by telephone only.

^c For a maximum of 2 years from the last dose, participants will be contacted by telephone every 3 months to determine their survival status.

^d Cancer history will include stage, date of diagnoses, and prior cancer therapies and procedures.

^e Pregnancy tests (serum or urine) will be performed at Screening (within 24 hours of first dose), on Day 1 of every cycle thereafter (within 24 hours of dose), and EOT.

^f Pulse oximetry will be collected with vital signs only at baseline.

^g Tumor markers (eg, CA19-9, PSA, etc) will be collected if performed as part of standard of care.

^h cfDNA (blood) will be assessed at Screening, preinfusion Cycle 2 Day 1, and EOT.

ⁱ Circulating soluble analytes and blood immune biomarkers will be assessed at Screening, preinfusion Cycle 1 Days 1 and 8, Cycles 2-4 Day 1, and EOT.

^j Stool collection will be assessed at Screening and at Cycle 2 Day 1, if possible. If this timing is not possible, any stool sample collected while on treatment would be acceptable.

^k Participants will undergo 3 tumor biopsies: mandatory baseline biopsy (for treatment assignment based on percent of tumoral CD8 cells), as early as possible after the 2nd dose of ipilimumab and after the 4th dose of ipilimumab (Day 2 – Day 10 of Cycle 2 and Cycle 6, respectively; however, any on treatment biopsy after Day 1 of Cycle 2 and Cycle 6 will be accepted, if medically feasible). Regardless of dosing, participants should continue to follow assessments as timed.

^l If the results of the baseline screening biopsy are not adequate to obtain information on the percentage of tumoral CD8 cells for treatment assignment, a 2nd baseline biopsy may be obtained, if it is medically feasible and the participant is willing to undergo another tumor biopsy. Additionally, if the results of the on treatment biopsy are not adequate to obtain information on the percentage of tumoral CD8 cells, a 2nd on treatment biopsy may be obtained, if it is medically feasible and the participant is willing to undergo another tumor biopsy.

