^m All AEs, SAEs, and all concomitant medications will be collected from the time the participant signs informed consent until 100 days after the last dose of study intervention. Prior to initiation of study intervention, only AEs and SAEs that are related to a protocol mandated intervention, including those that occur prior to assignment of study procedures (eg, screening invasive procedures, such as biopsies) should be reported. Trial-limiting toxicities can be found in [Section 8.3.7](#).

- ⁿ Nivolumab monotherapy will be administered at 360 mg IV Q3W for 4 cycles. Participants who continue to show clinical benefit after the first disease assessment will receive nivolumab at 480 mg IV Q4W until PD or intolerable toxicity (starting at Cycle 5).
- ^o Beginning at Cycle 7, nivolumab maintenance (nivolumab at 480 mg IV Q4W) will be administered until PD or intolerable toxicity.
- ^p Scans will be performed within 7 days prior to Day 1 of Cycle 4, Cycle 6, and every *even* cycle thereafter until death, disease progression, initiation of another systemic anticancer therapy, loss to follow-up, withdrawal of consent, or study termination, whichever occurs first (See [Section 8.1](#)). In addition, ad hoc scans, as part of standard of care, will be collected for participants who have discontinued treatment for reasons other than radiographic progression and prior to any alternate therapies.

Table 3: Schedule of Assessments Advanced Prostate Cancer (Nivolumab Only Arm: Nivolumab 360 mg Q3W and Maintenance 480 mg Q4W)

Tests & Procedures	Screening ^a	On-Treatment Evaluations				End of Treatment	Follow up ^b	
		C1		C2-4	C5 Onwards		15-30 days after last dose	First visit (90 days after last dose) ^b
Day	0	D1	D8	D1	D1			
Window (days)	-28 to 0	--	± 3	± 3	± 3	± 7	± 7	± 7
Informed consent ^a	X							
Medical, cancer history ^d	X							
Physical examination	X			X	X	X	X	
ECOG performance status	X			X	X	X	X	
Vital signs (see Section 8.2.3) ^e	X	X		X	X	X	X	
Body weight	X	X		X	X			
Hematology (see Table 10)	X		X	X	X	X	X	
Clinical chemistry (see Table 10)	X		X	X	X	X	X	
Urinalysis	X		X	X	X	X	X	
12-lead ECG	X							
PSA ^f	X	X	PSA will be collected every cycle throughout treatment			X		
ctDNA (blood) ^g	X			X ^g		X		
Circulating soluble analytes ^h	X	X	X	X		X		
Blood immune biomarkers ^h	X	X	X	X		X		
Stool collection ⁱ	X			X ⁱ				
Tumor biopsy ^j	X ^k			X ^j		X ^j		
Concomitant medications ^l	X	X	X	X	X	X	X	
Adverse events ^l	X	X	X	X	X	X	X	

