4.1.1 Advanced Prostate Cancer

1. Participants with advanced prostate cancer who are receiving nivolumab in combination with ipilimumab will be monitored for response and safety. Participants will undergo

on-treatment tumor biopsy procedures to assess immune markers according to the schedule:

- a. Within ± 3 days of the second dose of nivolumab (mandatory if medically feasible)
- b. A second biopsy, if medically feasible, should be obtained at Cycle 2 Day 22 (± 3 days of dose administration). An optional tumor biopsy sample may be collected upon disease progression.

The study design schema for advanced metastatic cancer are shown in [Figure 1](#) and [Figure 2](#) and for advanced prostate cancer are shown in [Figure 3](#) and [Figure 4](#).

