7 DISCONTINUATIONS OF STUDY INTERVENTION AND PARTICIPANT DISCONTINUATION/WITHDRAWAL

7.1 DISCONTINUATION OF STUDY INTERVENTION

Participants must discontinue study intervention if they experience any of the following:

- Intolerable toxicity related to study intervention, including the development of an AE determined by the Investigator to be unacceptable even with the participant's potential response to intervention due to the severity of the event
- Any medical condition that may jeopardize participant safety if he or she continues the study intervention
- Use of another anticancer therapy
- Symptomatic deterioration attributed to disease progression that per assessment by the Investigator necessitates discontinuation of study intervention.
- Radiographic disease progression per RECIST v1.1, unless the participant in the nivolumab monotherapy arm decides to enroll into the nivolumab and ipilimumab combination treatment arm (see [Appendix 3](#)). Refer to [Section 4.4](#) for description of treatment beyond progression.
- Pregnancy (see [Appendix 6](#))

Participants have the right to voluntarily withdraw from study intervention at any time for any reason. In addition, the Investigator has the right to withdraw a participant from study intervention at any time. Reasons for withdrawal from study intervention may include, but are not limited to, the following:

- Investigator or Sponsor determines it is in the best interest of the participant

- Participant noncompliance

The primary reason for study intervention discontinuation should be documented on the appropriate electronic case report form (eCRF) page.

The visit at which disease assessment shows PD may be used as the end of treatment visit. Participants who discontinue study intervention for any reason other than PD or loss of clinical benefit are to continue assessments as outlined in the Schedule of Activities (SOAs; see [Section 1.3](#)).

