**Table 2: Populations for Analysis**

| Population                                 | Description                                                                                                                                                                                                                      |
|--------------------------------------------|----------------------------------------------------------------------------------------------------------------------------------------------------------------------------------------------------------------------------------|
| Safety Population                          | All participants who received at least one dose of study drug. Participants will be analyzed according to the study intervention actually received.                                                                              |
| Modified Intent-to-Treat (mITT) Population | All participants with sufficient biopsy results to be assigned to a treatment arm and who received at least 1 dose of study drug. Participants will be analyzed according to the study intervention to which they were assigned. |
| On-treatment Biopsy Population             | All participants with at least 1 on-treatment biopsy with sufficient CD8 results will be included in the analyses of changes in CD8 counts.                                                                                      |

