#### 5.4.1 Primary Efficacy Endpoints

The co-primary endpoint of CBR will be reported among all participants within each study intervention group with a 95% credible interval assuming a beta (0.4, 1.6) prior. CBR is the proportion of participants who show clinical benefit, defined as CR, PR, or SD for  $\geq 6$  months as best response by RECIST v1.1 (Eisenhauer, 2009). Per RECIST, to be assigned a best overall response of complete response (CR) or partial response (PR), changes in tumor measurements must be confirmed by a repeat assessment that should be performed no less than 4 weeks after the criteria for response are first met. The duration of SD is defined as the time from the date of first dose of study intervention until the date of radiographic disease progression per RECIST. If no radiographic progression has occurred and the most recent tumor assessment with overall response of SD occurred  $< 6$  months after the date of first dose of study intervention, the participant will not have met the SD duration criterion and will not

be considered a CBR responder. Participants who do not have a disease assessment will be counted as not having clinical benefit.

For the second co-primary endpoint, the absolute change in the percentage of CD8 cells in on-treatment biopsies from baseline will be reported with a 95% credible interval with no prior for participants in the on-treatment biopsy population. In addition, the number of participants with baseline percentage of CD8 counts < 15% who “convert” from a cold to hot tumor (any on-treatment biopsy with percentage of CD8 counts  $\geq$  15%) will be summarized. The proportion of participants who convert from cold to hot will be reported with a 95% credible interval with no prior.

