**Table 3: Logistic Regression Model Parameters**

| Model number | Response variable (y) | Explanatory variable (x)                                                                              | Analysis Population            |
|--------------|-----------------------|-------------------------------------------------------------------------------------------------------|--------------------------------|
| 1            | CBR                   | Baseline percentage of CD8 cells                                                                      | mITT Population                |
| 2            | ORR                   | Baseline percentage of CD8 cells                                                                      | mITT Population                |
| 3            | CBR                   | Maximum percentage of CD8 cells across all on-treatment biopsies                                      | On-treatment Biopsy Population |
| 4            | ORR                   | Maximum percentage of CD8 calls across all on-treatment biopsies                                      | On-treatment Biopsy Population |
| 5            | CBR                   | Absolute change between baseline and maximum percentage of CD8 cells across all on-treatment biopsies | On-treatment Biopsy Population |
| 6            | ORR                   | Absolute change between baseline and maximum percentage of CD8 cells across all on-treatment biopsies | On-treatment Biopsy Population |
| 7            | CBR                   | CD8 Conversion Flag
(1 = CD8 converter, 0 = non-converter)                                         | On-treatment Biopsy Population |
| 8            | ORR                   | CD8 Conversion Flag
(1 = CD8 converter, 0 = non-converter)                                         | On-treatment Biopsy Population |

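### In the metastatic combination arm, taking the highest CD8 over all on-treatment biopsies gives participants with benefit more readings and biases the CD8-outcome association towards benefit

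*SAP*

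**What the plan says.** **Variable.** SAP Table 3, Models 3 and 4, regress CBR and ORR on "Maximum percentage of CD8 cells across all on-treatment biopsies". Models 5 and 6 use the change from baseline to that maximum, and Models 7 and 8 the conversion flag. SAP 5.4.1 defines conversion, from a baseline below 15%, by "any on-treatment biopsy with percentage of CD8 counts" of at least 15%. SAP 5.4.2.4 reports ORR and CBR among converters by the same rule.

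**Population.** SAP Table 2: "All participants with at least 1 on-treatment biopsy with sufficient CD8 results will be included in the analyses of changes in CD8 counts". One biopsy and two are treated alike.

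**Biopsies, metastatic combination arm.** Protocol 1.3, Table 2 footnote k, places them "as early as possible after the 2nd dose of ipilimumab and after the 4th dose of ipilimumab", meaning Cycle 2 and Cycle 6. A progression biopsy is optional (Protocol 4.1).

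**Scans, same arm.** "Cycle 4 Day 1, then beginning at Cycle 6 Day 1, repeat every 8 weeks" (Protocol 1.3, Table 2). Footnote p adds: "Scans will be performed within 7 days prior to Day 1 of Cycle 4, Cycle 6".

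**Who stays on schedule.** Protocol 7.1: "Participants who discontinue study intervention for any reason other than PD or loss of clinical benefit are to continue assessments". Footnote k also keeps assessments on time regardless of dosing.

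**Prostate combination cohorts.** Protocol 4.1.1: "A second biopsy, if medically feasible, should be obtained at Cycle 2 Day 22". The first scan is due at the same visit (Protocol 1.3, Table 4).

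Neither document adjusts for the number of biopsies, sets a landmark, or says whether a biopsy taken at progression counts as on-treatment.

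**The concern.** A participant with progression at the week 9 or week 15 scan cannot meet CBR through stable disease, which needs 6 months. The same participant normally also loses the Cycle 6 biopsy. One event thus helps settle both the response variable and the number of CD8 readings behind the explanatory variable. Because a maximum rises with the number of readings, CD8 can look associated with benefit when it is not.

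At stake are a stated secondary objective (association of CD8 infiltration with clinical outcome), the response rates quoted for converters, and the trial's rationale that turning cold tumours hot brings benefit. The error would favour that rationale. The co-primary any-biopsy conversion proportion also depends on how many biopsies each participant had.

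**Working it through.** **1. The plan's own figure.** Protocol 9.1 gives intervals for conversion with no prior. The posterior Beta(x, n - x) reproduces them: 16/160 gives 5.9% to 15.1%, and 80/160 gives 42.3% to 57.7%. The interval arithmetic is sound; the issue is what is counted.

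**2. Timing, metastatic combination arm (3-week cycles).**
- First biopsy, Cycle 2 Days 2-10: about weeks 3-4.
- Scan, Cycle 4 Day 1: 3 x 3 = week 9.
- Scan, Cycle 6 Day 1: 5 x 3 = week 15.
- Second biopsy, Cycle 6 Days 2-10: about weeks 15-16, after both scans.

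In the prostate combination cohorts (6-week cycles), Cycle 2 Day 22 is week 6 + 3 = 9. The second biopsy (within 3 days either side) and the first scan (up to 7 days before) fall together, so no earlier scheduled scan has removed progressors.

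**3. Size of the shift in the maximum.** For two standard-normal readings with correlation r, the expected maximum is sqrt((1 - r)/pi): 0.47 SD at r = 0.3 and 0.36 SD at r = 0.6. With no true association, the difference in mean between participants with and without benefit is (s1 - s0) times this, where s1 and s0 are the shares with a second biopsy.
- 90/10: 0.8 x 0.47 = 0.38 SD (r = 0.3) or 0.8 x 0.36 = 0.29 SD (r = 0.6).
- 60/40: 0.2 x 0.47 = 0.09 SD or 0.2 x 0.36 = 0.07 SD.

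**4. Conversion by any biopsy.** With chance q per independent biopsy, P(convert) = q + s(1 - q)q. Take q = 20% and the protocol's assumed CBR of 20%.
- Shares 70/30: 0.20 + 0.7 x 0.16 = 31.2% with benefit; 0.20 + 0.3 x 0.16 = 24.8% without. Odds ratio (0.312/0.688)/(0.248/0.752) = 1.38. CBR is 0.0624/0.2608 = 24% in converters and 0.1376/0.7392 = 19% in the rest.
- Shares 90/20: 34.4% against 23.2%, odds ratio 1.74, CBR 27% against 18%.

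Over q = 10-30% these odds ratios are 1.34-1.42 and 1.65-1.84. With correlation 0.5 between biopsies they fall to about 1.2-1.3 and 1.4-1.55.

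**5. False-positive rates.** Simulation with CD8 independent of benefit, CBR 20%, 100-130 participants biopsied, correlation 0.3-0.6, and a Wald test at an assumed two-sided 5% (the SAP names no level).

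| Variable | Second-biopsy shares, benefit / no benefit | False positives |
|---|---|---|
| Maximum (Model 3) | 90 / 10-50 | about 7-40% |
| Maximum (Model 3) | 70 / 30 | about 8-11% |
| Maximum (Model 3) | 70 / 50 or 60 / 40 | about 5-6% |
| Change to maximum (Model 5) | 90 / 10-50 | about 8-29% |
| Conversion flag (Model 7, 10% per biopsy) | 90 / 10-50 | about 6-13% |
| First biopsy only | all of the above | about 4-6% |

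Separate runs differ slightly: up to 12% at 70/30, and up to 16% for the flag. The ORR models (4, 6, 8) share these explanatory variables but were not simulated.

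**6. The opposite direction.** The monotherapy arm plans one on-treatment biopsy plus one at progression. If the latter counts, those without benefit gain the reading. At shares 30/50 the shift in the maximum is -0.2 x 0.47 = -0.09 SD (or -0.07 SD at r = 0.6). The flag formula gives the same direction: 24.8% against 28.0%, odds ratio 0.85 (0.81-0.92 in simulation). In that arm only the maximum and the change are affected, since tumours there start at 15% or more and cannot convert.

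**The case against.** **Stopping treatment is not the gate.** A reader might infer that the second biopsy reaches only participants still on treatment. It does not: Protocol 7.1 and footnote k keep those who stop for toxicity on schedule, and Protocol 4.4 lets some continue treatment past progression. This stands. The gate is progression or loss of clinical benefit, which is closer to the outcome, although treatment past progression and optional progression biopsies loosen it.

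**The prostate cohorts do not show the same selection.** This stands; see the timing above.

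**A late biopsy can still precede the outcome.** A reader might infer that a Cycle 6 value cannot predict response because a scan came first. The modelled outcome is best confirmed response or stable disease of at least 6 months (about week 26), and the objective is association. This stands against the stronger reading. It does not remove the unequal number of readings.

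**The size is assumed.** The documents give no second-biopsy shares, and on-treatment biopsies depend on medical feasibility. With nearly equal access the inflation is negligible. This stands, so 40% is the end of a range and not an expected value.

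**The study is exploratory.** SAP 5.4 disclaims hypothesis testing and type I error control. That answers a multiplicity complaint, but not a directional bias in estimates, Wald p-values and converter response rates that will still be reported. The any-biopsy proportion is a legitimate summary; its dependence on the number of biopsies needs to be visible.

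**Conclusion.** The point holds for the advanced metastatic combination arm, where most of the planned CD8 low participants are. Models 3-8 and the converter response rates are biased towards an association with benefit whenever participants with benefit have the Cycle 6 biopsy more often, and the schedule makes that likely. The direction follows from taking a maximum. The size rests on assumed shares, correlation and numbers biopsied: Model 3 false positives run from near nominal when access is similar to about 40% at the most unequal case examined.

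The documents do not support extending this at the same strength to the prostate combination cohorts, or assuming the same direction in the monotherapy arm, where the effect depends on whether progression biopsies count. The change is worth making before analysis, but it does not invalidate the trial.

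**What to change.** - **SAP Table 3, Models 3-8, and the converter ORR/CBR bullet in 5.4.2.4:** use the adequate biopsy from the first scheduled on-treatment time point as the main CD8 value, change and conversion flag. Allow a repeat for inadequacy if taken before the second time point.
- **Which biopsies count:** state that biopsies taken at progression are excluded. Leave participants whose only adequate sample is from the second time point out of these main models, and report how many there are.
- **SAP 5.4.1:** report conversion at each scheduled time point with the number biopsied, beside the any-biopsy figure. Tabulate number of biopsies by CBR status, so that the shares assumed here can be replaced by observed ones.
- **Maximum-based models:** keep as descriptive, labelled as affected by this selection. The second-biopsy value may be shown separately among those progression-free at that time.

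The cost is SAP wording and a few table rows, with no new data. The downside is that conversions seen only at the second biopsy, which that biopsy was partly meant to capture, leave the main association models. They are still reported by time point.
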